Endpoint(s)	
Primary outcome measure: The primary outcome will be the difference in accuracy between LDCT and CXR, assessed at the end of the ED evaluation, using the expert panel as the reference standard, accuracy being computed as $(\text{true positive} + \text{true negative cases}) / (\text{true positive} + \text{true negative} + \text{false positive} + \text{false negative cases})$.
 
Main secondary outcome measures: Diagnostic outcomes: 
 • Proportion of patients with an adequate diagnosis using LUS compared to CXR • Proportion of patients with an adequate diagnosis using LUS compared to LDCT 

	
 • Proportion of patients with an alternative diagnosis • Number of additional imaging studies and invasive procedures prescribed during the acute setting • Prevalence of unmasked imaging results (for an emergency finding) • Prevalence of incidentalomas 
Treatment outcomes:
 
 • Number of antibiotic free days at day 30 
Clinical outcomes:
 
 • Time to clinical stability during the first 2 weeks • Length of hospital stay • Proportion of patients with an unplanned transfer to the ICU or operating room • Proportion of patients admitted to rehabilitation or long-term care facility (LTCF) days through 3 months • All-cause mortality through 1 month and 3 months • All-cause readmission to the acute care setting through 1 month and 3 months • Quality of life at admission, discharge and 3 months 
Agreement for the diagnosis of pneumonia between clinicians and a panel of experts
 
Association between biological markers (C-reactive protein and procalcitonin) and the presence of an infiltrate
 
Cost outcomes:
 
Costs of care, physician, imaging, laboratory, treatment (including antibiotic therapy) and others per patient, health related quality of life until 3 months; unit of work consumption per hospital (number of minutes of care, physician, laboratory and imaging points)
 
Safety outcomes: unplanned transfer to the ICU after initial admission; 1-month mortality.
 
GEROBIOTA
 
The probability of pneumonia/aspiration pneumonia according to the panel of experts; Proportion of patients admitted to rehabilitation or LTCF days through 3 months; all-cause mortality through one-year; all-cause readmission to hospital or LTCF through one-year.

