3. STUDY OBJECTIVES AND DESIGN

3.1 Hypothesis and primary objective

Overall aim: To compare the diagnostic, therapeutic and clinical outcomes of three diagnostic strategies based on CXR (standard care), low-dose CT scan (LDCT) or lung ultrasonography (LUS) in elderly patients with suspected community or nursing-home acquired pneumonia in the ED.

Primary objective: To evaluate whether a diagnostic strategy using LDCT compared with CXR leads to a more accurate diagnosis in suspected pneumonia.

Secondary objectives:

Diagnostic objectives:

- To assess the difference in diagnostic accuracy for patients with suspected pneumonia using LUS compared to CXR, and using LUS compared to LDCT
- To assess sensitivity and specificity of CXR, LDCT and LUS; the number of additional imaging studies and invasive procedures prescribed during the acute setting; the imaging studies needing unmasking in emergency; the incidentalomas.

Treatment objectives: to assess whether there is a difference between the diagnostic strategies in:

- Antibiotic consumption up to one month

Clinical objectives: to assess whether there is a difference between the diagnostic strategies in:

- Time to clinical stability
- Length of hospital stay

- Unplanned transfer to the intensive care unit or operating room
- Admission to rehabilitation/long-term care facility (LTCF) up to 3 months
- All-cause mortality up to 3 months
- All-cause readmission up to 3 months
- Quality of life at admission, discharge and 3 months

Cost outcomes

Diagnosis concordance between physicians at the ER and experts

The association of biomarkers and the presence of an infiltrate.

GEROBIOTA objectives

To identify factors associated with the probability of pneumonia, and aspiration pneumonia, 1 month and 1 year mortality, 1 year readmission and to create a biobank allowing the assessment of inflammation, immune status and genetic markers.

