3.2 Primary and secondary endpoints

Primary outcome measure:

The primary outcome will be the difference in accuracy between LDCT and CXR, assessed at the end of the ED evaluation, using the expert panel as the reference standard, accuracy being computed as (true positive + true negative cases) / (true positive + true negative + false positive + false negative cases).-

Main secondary outcome measures:

Diagnostic outcomes:

- Difference in accuracy between LUS and CXR, assessed at the end of the ED evaluation, using the expert panel as the reference standard
- Sensitivity, specificity of CXR, LDCT and LUS
- Number of additional imaging studies and invasive procedures prescribed during the acute setting
- Prevalence of viral pneumonia
- Prevalence of unmasked imaging results (for an emergency finding)
- Prevalence of incidentalomas

Treatment outcomes:

- Number of antibiotic free days at day 30

Clinical outcomes:

- Time to clinical stability during the first 2 weeks (number of days from admission to the first time all of the following parameters are above/under the threshold value and maintained for a minimum of 24 hours: heart rate <100 beats/min, systolic blood pressure >90 mmHg, temperature <37.8°C (axillary or tympanic), respiratory rate <24 breath/min, oxygen saturation >90% while breathing room air, or need for more than 28% fraction of inspired oxygen to maintain adequate oxygen saturation, resolution of delirium if present at admission)
- Length of hospital stay (in the ED and in the acute setting)
- Proportion of patients with an unplanned transfer to the ICU
- Proportion of patients admitted to rehabilitation or LTCF days through 3 months
- All-cause mortality through 1 month and 3 months
- All-cause readmission to the acute care setting through 1 month and 3 months
- Quality of life at admission, discharge and 3 months (measured by EQ-5D-3L and a CAP score questionnaire)
 - Interagreement rate for the probability of pneumonia between physicians participating to the trial and a consensus of experts in chest imaging, for each method

- Association between biological markers (CRP and PCT) and the presence of an infiltrate

Cost outcomes:

Costs of care, physician, imaging, laboratory, treatment (including antibiotic therapy) and others per patient, health related quality of life until 3 months; unit of work consumption per hospital (number of minutes of care, physician, laboratory and imaging points)

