Safety outcomes: unplanned transfer to the ICU; 1-month mortality.

[figure not shown]
GEROBIOTA:

The probability of pneumonia/aspiration pneumonia according to the panel of experts, all cause 1 month and 1 year mortality, 1 year readmission for pneumonia.

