8) Clinical outcomes: We will use Kaplan Meier's estimates to evaluate the time to clinical stability over 15 days in each arm, and a log-rank to compare them. Patients who die in the first 2 weeks will be censored at day 15 (i.e. considered has never reaching clinical stability). The Mann-Whitney test will be used to compare the length of hospital stay between the groups. The proportion of patients with an unplanned transfer to the ICU or operating room will be reported by arm and compared between the arms using a logistic regression model adjusted for sites. All-cause mortality during the 3-month follow-up will be investigated with Kaplan Meier's survival curves, and compared between the arms using a log-rank test stratified on sites. Readmissions during the 3-month follow-up will be investigated using survival models with competing risk. Death before readmission will be the competing event.

9) Cost outcomes: Mean cost per patient will be assessed and compared between arms using multiple linear regression models adjusted for sites. Reweighted estimators will be used to account for censoring.

10) Interagreement rate for the probability of pneumonia rated on a 3-level Likert scale: the agreement between raters participating to the trial and a consensus of two experts will be investigated by using kappa statistics.

11) The association between biological markers (CRP and PCT) and infiltrates will be assessed by differences in the mean levels of markers between patients with and without infiltrates and tested by using t test. Transformations on markers will be applied if needed. Multiple linear regression models will be used for adjustment. Similar methods will be used to investigate the association between markers and the probability of pneumonia rated on the 3-level scale. The analyses will be conducted for each arm.

Interim and safety analyses

There will be no comparative analysis for efficacy or futility. An initial safety analysis will be performed after 200 patients have reached the 1-month follow-up. The study's data manager will ensure that the data will be exported with "scrambled" allocation labels and that study investigators do not have access to the data. The results will be transmitted to the principal investigators and the safety monitoring board. The latter will be free to lift the blind if deemed necessary, and will be asked to make the final decision on the continuation of the study without modification, or terminating the study.

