#### 8.1.2.4 Clinical outcomes

- **Number of days requiring oxygen therapy** will be analysed for descriptive purposes only.
- **Length of stay (in the acute care setting)** will be calculated as the number of days between the emergency entry date (*emergencydate*) and the hospital discharge date (*hospital\_discharge\_date*)
  - A stay of 1 day corresponds to admission and discharge on the same calendar day.
  - A stay of 2 days corresponds to discharge on the day after admission, and so on.
- **Discharge after emergency** will be defined as a hospital stay of 1 day – that is, when the emergency entry date (*emergencydate*) and the hospital discharge date (*hospital\_discharge\_date*) fall on the same calendar day.
- **Transfer to the ICU/IMCU within 30 days** after the initial emergency admission/evaluation will be considered as having occurred if **either** of the following conditions is met:
  - The time between emergency entry date (*emergencydate*) and the hospital discharge date is  $\leq 30$  days **and** the discharge destination (*discharge\_place*) is ICU or IMCU; or
  - The 1-month follow-up visit reports a transfer to ICU (*transfer\_to\_icu*) or IMCU (*transfer\_imcu*), **and** the delay between the emergency entry date (*emergencydate*) and the ICU/IMCU admission date (*icu\_transfer\_date* or *imcu\_transfer\_date*) is  $\leq 30$  days
- **Transfer to a rehabilitation unit within 90 days** after the initial emergency admission/evaluation will be considered as having occurred if **either** of the following conditions is met:
  - The discharge destination (*discharge\_place*) is rehabilitation and the delay between *emergencydate* and *hospital\_discharge\_date* is  $\leq 90$  days; or
  - A transfer to rehabilitation (*rehabilitation*) with a corresponding admission date (*rehabilitation\_date*)  $\leq 90$  days after *emergencydate* is reported at the 1- or 3-month follow-up.
- **Transfer to a long-term care facility (LTCF) within 90 days** after the initial emergency admission/evaluation will be considered as having occurred if **either** of the following conditions is met:

- The discharge destination (*discharge\_place*) is LTCF and the delay between *emergencydate* and *hospital\_discharge\_date* is  $\leq$  90 days; or
- A transfer to LTCF (*transfer\_ltcf*) with a corresponding admission date (*ltcf\_transfert\_date*)  $\leq$  90 days after *emergencydate* is reported at the 1- or 3-month follow-up.

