#### 8.2.3.4 Clinical outcomes

- **All-cause mortality at 30 days** will be
  - estimated by arm using the Kaplan-Meier method
  - compared between arms through pairwise comparisons using a log-rank test stratified by centre (three pairwise tests will be performed)
  - and the complementary log-log transformation will be applied to calculate the 95% confidence intervals for the 30-day survival estimates
- **All-cause mortality at 30 days** will be described only
- **In-hospital mortality**
  - will be described by arm as count and percentages
  - will be compared between arms using a logistic regression model adjusted on centre. Odds ratio will be reported with 95% confidence intervals
- Number of patients hospitalised after emergency and number of patients discharged after emergency will be described by arm as count and percentages
- **Length of hospital stay**
  - Will be analysed **among all randomized patients, and repeated among hospitalized patients only** (excluding those discharged after emergency department presentation)
  - Will be compared between arms using a linear regression model adjusted on centre with a bootstrap method for 95%CI.
  - Pvalues will be computed by inverting the corresponding confidence interval (Thulin 2024: modern statistics with R).
- **Unplanned transfer to the ICU/IMCU within 30 days after initial admission/evaluation**
  - Will be analysed **among all randomized patients, and repeated among hospitalized patients only** (excluding those discharged after emergency department presentation)
  - Will be described by arm as count and percentages
  - Will be compared between arms using a logistic regression model adjusted on centre. Odds ratio will be reported with 95% confidence intervals.
- The following outcomes will be described by arm as count and percentages **in patients discharge alive**. Those outcomes will not be compared between arms:
  - **Admission to rehabilitation through 3 months in patients discharge alive**
  - **Transfer to LTCF through 3 months in patients discharge alive**
  - **All-cause readmission to acute care setting in patients discharge alive**
  -
- The **quality of life 30 days and 90 days** will be described by arm as median and IQR **in patients discharge alive**. Quality of life will not be compared between arms

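### The SAP never compares the protocol's safety outcome, unplanned ICU transfer, between arms: it substitutes an undeclared ICU/IMCU composite with no rule for 'unplanned'

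*SAP*

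**What the plan says.** **Protocol, safety outcome.** The synopsis (Endpoints) gives "Safety outcomes: unplanned transfer to the ICU after initial admission; 1-month mortality". Section 3.2 gives "Safety outcomes: unplanned transfer to the ICU; 1-month mortality". Neither mentions intermediate care or the operating room, and neither sets a time window for the transfer. Section 4.3 has deaths and ICU admissions by arm going to the safety board, and section 7.1 has the board judging ICU transfer and mortality.

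**Protocol, secondary clinical outcome.** This is a separate item. The synopsis has "Proportion of patients with an unplanned transfer to the ICU or operating room", section 3.1 has "Unplanned transfer to the intensive care unit or operating room", and section 5.1 plans that "unplanned transfer to the ICU or operating room will be reported by arm and compared between the arms". The endpoint list in section 3.2 has only "Proportion of patients with an unplanned transfer to the ICU", so the protocol does not agree with itself about the operating room.

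**SAP.** Section 1 says the document was finalised after enrolment and before analysis. The outcome summary in 3.3.2 lists ICU admission. Section 8.1.2.4 defines "Transfer to the ICU/IMCU within 30 days" from the discharge destination or from ICU and IMCU transfer dates recorded at the 1-month visit, with no 'unplanned' condition. Section 8.2.3.4 compares "Unplanned transfer to the ICU/IMCU within 30 days after initial admission/evaluation" by logistic regression adjusted for centre. The operating room appears nowhere. Section 9 declares the addition of in-hospital mortality and two subgroups and the removal of time to clinical stability, and nothing on this outcome.

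**The concern.** Protocol section 6.2 plans no documentation of non-serious adverse events, so ICU transfer and 1-month mortality carry most of the comparative safety evidence. Followed as written, the SAP produces a between-arm comparison for an outcome the protocol did not name and none for the one it did. The final report would also not match what the safety board was asked to watch. A change to a named safety outcome made after enrolment should be declared, whichever way it moves the estimate.

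Two further points follow from the wording. First, intermediate care is a lower level of escalation, and its addition could weaken an ICU difference. Second, the 8.1.2.4 rule accepts any qualifying ICU or IMCU date within 30 days of ED entry. The eligibility criteria exclude patients who need immediate ICU admission but not those who go from the ED to IMCU. Such a first admission may therefore be counted as an unplanned transfer, whereas the protocol synopsis requires the transfer to come after initial admission.

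**Working it through.** **1. The definitions side by side**

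| Place | Destination | 'Unplanned' |
|---|---|---|
| Protocol synopsis, safety | ICU | yes, after initial admission |
| Protocol 3.2, safety | ICU | yes |
| Protocol synopsis, 3.1 and 5.1, secondary clinical | ICU or operating room | yes |
| Protocol 3.2, secondary clinical | ICU | yes |
| SAP 3.3.2 | ICU | not stated |
| SAP 8.1.2.4 | ICU or IMCU, 30 days | no condition |
| SAP 8.2.3.4 | ICU or IMCU, 30 days | in the title only |

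The three SAP entries differ from one another, and neither the definition nor the analysis entry matches the protocol's safety outcome.

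**2. Check of the formula against the plan's own figure**

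The documents give no power figure for ICU transfer. The only one available is the primary sample size (SAP 3.5): accuracy 68% v 84%, two-sided alpha 0.05, power 90%, 150 per arm.

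n = [1.96·√(2·0.76·0.24) + 1.2816·√(0.68·0.32 + 0.84·0.16)]² / 0.16² = (1.184 + 0.760)² / 0.0256 = 148 per arm.

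This is close to the stated 150, so the same pooled two-proportion formula is used below. The point does not depend on it.

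**3. What adding IMCU does to power (assumed rates)**

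Power = Φ[(|p2 − p1| − 1.96·se0)/se1], where se0 = √(2·p̄(1 − p̄)/n), se1 = √((p1(1 − p1) + p2(1 − p2))/n) and n = 165 (SAP 3.5 recruitment target).

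Worked example, ICU 4% v 8%: p̄ = 0.06, se0 = 0.02615, se1 = 0.02605. (0.04 − 1.96 × 0.02615)/0.02605 = −0.43, so power = 0.33.

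Add IMCU-only transfers at the same rate in both arms:

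| IMCU-only rate, both arms | Event rates | Odds ratio | Power |
|---|---|---|---|
| none | 4% v 8% | 2.09 | 0.33 |
| 3% | 7% v 11% | 1.64 | 0.24 |
| 5% | 9% v 13% | 1.51 | 0.21 |
| 10% | 14% v 18% | 1.35 | 0.17 |

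Now let IMCU-only transfers differ as well, at 10% in the lower arm. An IMCU-only risk ratio of 1.25 gives 14% v 20.5% and power 0.35. A ratio of 1.5 gives 14% v 23% and 0.56. A ratio of 2.0 gives 14% v 28% and 0.88.

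The break-even IMCU-only risk ratio, above which the composite is the more powerful test, is 1.31, 1.28 and 1.24 at IMCU-only rates of 3%, 5% and 10%. With other assumed ICU pairs (2% v 6%, 3% v 8%, 5% v 10%) it lies between 1.24 and 1.48.

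**The case against.** The best case for the SAP has four parts.

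- **The direction of the effect is unknown.** If a missed diagnosis leads to deterioration, IMCU use may rise with ICU use, and the composite would then be more sensitive. This stands. A reader might infer that the composite dilutes or masks an ICU signal. The documents give no rates to support that, and modest changes in the assumptions reverse it. ICU-only is not well powered either: at 4% v 8% it misses a doubling two times in three, and the trial was sized only for accuracy.
- **ICU information is not lost.** The safety board was to receive ICU admissions by arm, SAP 8.2.1 tabulates ICU and IMCU separately as discharge places, and SAP 8.5 describes safety outcomes by arm. This stands, but none of it is a planned comparison of ICU transfer.
- **The operating room was not in the safety outcome.** A reader might infer that it was removed from there. Both protocol statements of the safety outcome omit it. It belonged to the secondary clinical outcome, and protocol 3.2 already leaves it out of that. What remains is an undeclared omission from an outcome on which the protocol is inconsistent.
- **Counting of ED-to-IMCU admissions is not certain.** It depends on how sites complete the transfer fields, and those instructions are not in the documents. The admissions may count; the text does not show that they do.

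None of this answers the mismatch between protocol and SAP or the silence of section 9.

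**Conclusion.** The point holds as a mismatch in definition and reporting. The protocol's safety outcome has no planned between-arm comparison, the substitute includes intermediate care and has no operational rule for 'unplanned', the SAP's own three descriptions disagree, and section 9 declares none of it. The operating-room omission is a separate and smaller item of the same kind.

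The size of any effect on the safety conclusion is not determined. Under an assumed ICU rate of 4% v 8%, power moves from 0.33 to between 0.17 and 0.24 if IMCU-only transfers are equal across arms. It rises above 0.33 if their risk ratio exceeds about 1.2 to 1.3 (up to about 1.5 under the other ICU rates tried). These figures are illustrations. The documents also give no ground for inferring that the change was driven by results, since the SAP states that it precedes analysis.

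**What to change.** 1. In SAP 8.1.2.4 and 8.2.3.4, compare ICU-only transfer between arms as the protocol's safety outcome, using `transfer_to_icu` with `icu_transfer_date`, or `discharge_place` = ICU, within the SAP's 30-day window. Keep ICU/IMCU as an additional outcome.
2. State how 'unplanned' and 'after initial admission' are ascertained from the collected data, including how a first admission from the ED to IMCU is handled. The protocol does not define 'unplanned', so it cannot simply be cited. If the data cannot support the distinction, drop the word and say so.
3. Make SAP 3.3.2, 8.1.2.4 and 8.2.3.4 describe the same outcomes.
4. In section 9, list the IMCU addition and the omission of the operating-room component, noting that the protocol sections differ on the latter.

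The cost is one table row and a few sentences. ICU and IMCU transfers already have separate fields, so nothing new needs to be collected for the ICU-only row. That row will have few events (at 4% v 8% with 165 per arm, 165 × 0.04 = 6.6 and 165 × 0.08 = 13.2 expected) and a wider interval for the odds ratio than the composite.

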- **All-cause mortality within 30 days** will be defined as a death date (*death\_date* or *deathdate*) occurring within **30 days** of the emergency entry date (*emergencydate*)

- **All-cause mortality within 90 days** will be defined as a death date (*death\_date* or *deathdate*) occurring within **90 days** of the emergency entry date (*emergencydate*)

- **In-hospital mortality** will be defined as a death occurring on or before the hospital discharge date (*hospital\_discharge\_date*), based on the recorded death date (*death\_date* or *deathdate*)

- **All-cause readmission within 90 days** after initial emergency admission/evaluation will be defined as a readmission date (*readmission\_date*) occurring within **90 days** of the emergency entry date (*emergencydate*)

- **Quality-of-life at 30 days and 90 days** (*eq5d\_score*)

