**Antibiotic prescription, n/N (%)**

Indication  
Pneumonia  
Acute bronchitis  
Exacerbation of COPD  
Urinary tract infection  
Other

At hospital discharge  
Place of discharge  
Rehabilitation  
Home  
LTCF  
ICU  
IMCU

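### For patients recorded as discharged to ICU or IMCU, the hospital discharge date is the date of that move, so length of stay ends there and later ICU/IMCU deaths are not counted as in-hospital deaths

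*SAP*

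**What the plan says.** SAP 8.1.2.4 gives two routes by which an ICU/IMCU transfer within 30 days is counted.

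- **First route.** There is a limit of 30 days on an interval ("The time between emergency entry date (*emergencydate*) and the hospital discharge date is"), and the recorded discharge destination "is ICU or IMCU; or".
- **Second route.** "The 1-month follow-up visit reports a transfer to ICU" or IMCU, with its own date field (`icu_transfer_date` or `imcu_transfer_date`).

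The baseline table in SAP 8.2.1 agrees with the first route. Under "Place of discharge" it lists rehabilitation, home, LTCF, ICU and IMCU.

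The same section uses `hospital_discharge_date` for three further purposes:

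- Length of stay in acute care "will be calculated as the number of days between the emergency entry date" and `hospital_discharge_date`, with same-day discharge counted as 1 day.
- Discharge after emergency is a stay of 1 day.
- In-hospital mortality "will be defined as a death occurring on or before the hospital discharge date".

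Under SAP 8.2.3.4, in-hospital mortality "will be compared between arms using a logistic regression model adjusted on centre". Length of stay is compared by linear regression adjusted for centre. Length of stay and ICU/IMCU transfer are analysed in all randomised patients and again without those discharged after emergency. Rehabilitation, LTCF, readmission and quality of life are described among patients discharged alive (for example "All-cause readmission to acute care setting in patients discharge alive"). That group has no definition of its own.

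**The concern.** One date field carries two meanings. For a patient whose `discharge_place` is home, it marks the end of acute care. For a patient whose `discharge_place` is ICU or IMCU, the first route works as a transfer rule only if the field marks the day of the move, when acute care continues at a higher level. Nothing in the SAP carries the stay, or the window for in-hospital death, through the ICU/IMCU period. The note at the end of 8.1.2.4, on taking the earliest date when an event is reported at several visits, does not do so.

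Two between-arm comparisons are at stake. The error depends on escalation of care, which the imaging strategy could influence. If one arm has more moves recorded this way, its stays are cut more often and more of its later ICU/IMCU deaths go uncounted. Both errors make that arm look better. The result also depends on which field a site filled in, not only on what happened to the patient.

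**Working it through.** The plan states no figure on this point, so there is none to reproduce. The check applies the rules of SAP 8.1.2.4 literally to example patients, with emergency entry on day 0.

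**Rules**

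- Length of stay = (discharge day − entry day) + 1.
- In-hospital death = yes if death day ≤ discharge day.
- Discharge after emergency = yes if length of stay = 1.

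**Example patients (invented for illustration)**

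| Course | Recording | Length of stay | In-hospital death | Discharge after emergency |
|---|---|---|---|---|
| ICU day 3, dies in ICU day 8 | First route, discharge = day 3 | 3 + 1 = 4 | 8 ≤ 3: no | no |
| Same course | Second route, discharge dated at death | 8 + 1 = 9 | 8 ≤ 8: yes | no |
| ICU day 3, survives, leaves acute care day 15 | First route, discharge = day 3 | 4 | no | no |
| Same course | Second route, discharge = day 15 | 15 + 1 = 16 | no | no |
| ICU same day, dies day 5 | First route, discharge = day 0 | 0 + 1 = 1 | 5 ≤ 0: no | yes |

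The second row assumes that sites enter the date of death as the discharge date, which the documents do not state. In the last row the patient counts as an ICU transfer among all randomised patients but is dropped from the hospitalised-only analyses of length of stay and of ICU/IMCU transfer. By the only in-hospital death rule given, the patients in rows one and five would also fall among those discharged alive.

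**Scale**

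Input from the documents: 165 patients per arm (SAP 3.5). Assumed, because the documents give no figures:

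- 2–10% of patients moved to ICU/IMCU;
- 25–100% of these moves recorded by the first route;
- 20–40% of moved patients dying later in the same acute stay;
- 5–12 hospital days lost per truncated stay.

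Uncounted in-hospital deaths per arm = 165 × share moved × share dying × share by first route.

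- Low: 165 × 0.02 × 0.20 × 0.25 = 0.165, about 0.2.
- High: 165 × 0.10 × 0.40 × 1.00 = 6.6.

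Fall in an arm's mean length of stay, if all moves go by the first route = share moved × days lost.

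- Low: 0.02 × 5 = 0.1 day.
- High: 0.10 × 12 = 1.2 days.

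Only the difference between arms biases a comparison. For example, a 5-point difference in first-route moves with 10 days lost each (both assumed) shifts the difference in means by 0.05 × 10 = 0.5 day, in favour of the arm with more moves.

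**The case against.** The strongest reply is that this may concern very few patients. The second route has its own date fields, and a transfer recorded only there need not shorten the stay. The case report form, which would settle what `hospital_discharge_date` holds, is not in the documents. Patients needing immediate ICU admission are excluded (Protocol 4.1), and the protocol says severe pneumonia is not included (3.3), so moves may be uncommon. All of this stands, and it limits the size. It does not remove the defect. The first route and the baseline table both provide for ICU/IMCU as a discharge place, and no rule then extends the stay. If the destination is another hospital's ICU, the patient is still in acute care, and Protocol 3.2 describes length of stay as time in the ED and the acute setting.

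A reader might infer that the plan would hide deterioration or harm in an arm. The documents do not support that. The protocol's safety outcomes are unplanned ICU transfer and 1-month mortality (3.2). Transfer in all randomised patients counts both routes. Mortality at 30 and 90 days runs from emergency entry and does not use the discharge date.

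A reader might also infer that a large share of in-hospital deaths would be lost. That would need both the number of first-route moves and the true number of in-hospital deaths, and the documents give neither.

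The affected outcomes are also of lower rank. SAP 9 lists in-hospital mortality as an exploratory addition. The summaries in patients discharged alive are descriptive only, and a patient who dies in ICU on day 8 contributes no day-30 or day-90 quality-of-life value.

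**Conclusion.** The definitions give a wrong result for patients with `discharge_place` = ICU or IMCU, and only for them. Their length of stay ends at the move, their deaths on a later calendar day in ICU/IMCU are not in-hospital deaths, and a same-day move is treated as a discharge from the emergency department. A death on the calendar day of the move is still counted. This touches one protocol-specified secondary comparison (length of stay), one exploratory comparison (in-hospital mortality), the repeat analysis of ICU/IMCU transfer in hospitalised patients, and some descriptive denominators.

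The direction is clear: both outcomes are understated in an arm with more such moves. The size is not known. The ranges of 0.2 to 6.6 deaths per arm and 0.1 to 1.2 days rest wholly on the assumed rates, and the low end is negligible. The primary outcome is untouched. The point should be corrected before lock because following the rules as written misclassifies identifiable patients and the remedy is cheap.

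**What to change.** In SAP 8.1.2.4, define an end-of-acute-care date: the date of live discharge to home, LTCF or rehabilitation, or the date of death if earlier, with any ICU/IMCU stay included. Use it for length of stay, in-hospital death, discharged alive and discharge after emergency. State that `discharge_place` = ICU or IMCU does not end the stay. The first-route rule for counting an ICU/IMCU transfer can remain, using the existing field as the date of the move.

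Before database lock, list the patients with `discharge_place` = ICU or IMCU by arm and query the final acute-care discharge date for those patients only. If there are none, the change costs a sentence of wording. Otherwise the cost is a small data query. Since enrolment is complete, it may need source retrieval at the centres if the database does not hold that date. No new patients or procedures are needed.
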